9.4 Futility Analysis Simulation Report

1.0 Background

This is a Phase 3 study of mirabegron in subjects with an Overactive Bladder (OAB). The study includes mirabegron and placebo. The primary efficacy endpoint is the change from baseline in mean number of micturitions per 24 hours at the end of the 12-week treatment period for children (week 12/EoT). A negative change from baseline is considered a beneficial effect. A total sample size of 184 evaluable subjects will be randomized in a 1:1 ratio to the two treatment groups. It is expected that 164 subjects will be evaluable for the primary analysis. For the calculations it is assumed that 82 subjects per arm are evaluable.

2.0 Interim Evaluation

One comparative interim evaluation is planned to take place when 50%, i.e., 41 per treatment arm, of planned subjects to be randomized have had their week 12/EoT assessment. The intent of planning and conducting an interim efficacy analysis is to evaluate whether the mirabegron group meets futility criteria.

At the interim evaluation, a Bayesian predictive probability for the event of a final 1-sided p-value ≤ 0.05 will be calculated, comparing the mirabegron group with placebo. If the predictive probability for the interim evaluation is ≤ 0.05 (i.e., there is a $\leq 5\%$ chance of obtaining a statistically significant result for the primary efficacy analysis for mirabegron group at the final analysis), the mirabegron will be considered to have met futility criteria.

2.1 Decision Rule for Futility

At the interim evaluation, the following predictive probability will be calculated:

Predictive Probability of ({final 1-sided p-value of mirabegron vs. placebo ≤ 0.05 } | Data).

Given the data at the interim analysis, a predictive probability of a positive study will be calculated. A positive study is defined as the final 1-sided p-value ≤ 0.05 when comparing mirabegron vs. placebo in the primary efficacy analysis. If the predictive probability is no more than 0.05 at this interim evaluation, the study will be recommended to stop for futility. Otherwise, the study will continue.

2.2 Calculation of Predictive Probability

At the interim evaluation, the predictive probability is expressed as an integration of the probability of {final one-sided p-value of mirabegron vs. placebo ≤ 0.05 } over the posterior distribution of the treatment difference given the observed data:

 $\int \Pr(\{\text{Final one-sided } p \text{ - value} \le 0.05\} | \theta) \times \Pr(\theta | \text{data}) d\theta,$

where θ stands for the difference in mean change from baseline to week 12/EoT in mean number of micturitions per 24 hours between mirabegron group and placebo group. Such predictive probability can be computed through simulation.

Since we use non-informative prior distribution of difference in mean change from baseline to week 12/EoT in mean number of micturitions per 24 hours between mirabegron group and

placebo group, it is assumed that the mean number of micturitions per 24 hours follows a Normal distribution and equal sample size per arm at the interim evaluation, the Bayesian predictive probability for the event of a final 1-sided p-value of mirabegron vs. placebo ≤ 0.05 (denoted by *PP*) can be calculated using a closed form based on the methods described in Geisser and Johnson (1994), Dmitrienko and Wang (2006).

$$PP = \Phi\left[\frac{1}{\sqrt{M}}\left(\sqrt{N+M} Z_N - \sqrt{N} Z_{0.95}\right)\right]$$
(1)

where

 Φ stands for the cumulative distribution function for the standard normal distribution;

N = number of subjects per arm observed at the interim evaluation, here N=41;

M = number of subjects per arm as yet unobserved at the interim evaluation, here M = 82 - N

 Z_N = test statistic, where the numerator (difference in mean change between mirabegron and placebo) will be obtained from the sample means of the mirabegron group and placebo group,

$$Z_N = \frac{\text{Difference in LS mean change (mirabegron - placebo)}}{\sigma \sqrt{\frac{2}{N}}}$$
(2)

The least squares (LS) means for placebo group and mirabegron group will be obtained from the ANCOVA with treatment (mirabegron and placebo), visit, geographical region, sex, and treatment by visit interaction as fixed effects and baseline value (mean number of micturitions per 24 hours at baseline) as covariate. The estimated pooled standard deviation (σ) will also be obtained from the same ANCOVA model.

3.0 Simulation Algorithm

Simulations were conducted to evaluate the operating characteristics of this design, including the probability of meeting the futility criteria at the interim evaluation, and the probability of continuing to the end and having final 1-sided p-value ≤ 0.05 .

Change from baseline to week 12 in mean number of micturitions per 24 hours for each subject is generated from a Normal distribution. The common standard deviation for mirabegron group and placebo group is fixed at 2.3 (see Section 3, Sample Size). The planned sample size is 82 subjects per arm. The scheduled interim evaluation is the moment when 82 subjects (i.e., 41 subjects per arm) have their week 12/EoT mean number of micturitions per 24 hours. The outcome of the simulation is based on 50,000 runs (i.e., repeated trials).

Six (6) scenarios were evaluated. Each scenario specifies a mean change from baseline to week 12 in mean number of micturitions per 24 hours in the mirabegron group, while it keeps the mean change from baseline to week 12 in mean number of micturitions per 24 hours for placebo group fixed as -0.9.

See Table 7.1-1 for the six scenarios, where δ denotes the treatment difference between mirabegron group and placebo group in mean change from baseline to week 12 mean number of micturitions per 24 hours and a negative value of δ indicates a favorable treatment effect, and μ_A denotes the corresponding mean change from baseline to week 12 in mean number of micturitions per 24 hours for mirabegron group.

Scenario #	1	2	3	4	5	6
CfB for mirabegron	-0.9	-1.1	-1.3	-1.5	-1.7	-1.8
δ*	0.0	-0.2	-0.4	-0.6	-0.8	-0.9

 Table 7.1-1:
 Simulation Scenarios

CfB: Change from Baseline

*: Treatment difference (δ) = mirabegron – placebo. Negative value of δ indicates favorable treatment effect. σ = 2.3 for both treatment groups.

The simulation steps are as follows:

- 1. Generate 41 observations from a Normal distribution with mean = 0.0 and standard deviation = 2.3 for placebo group and 41 observations from a Normal distribution with mean δ (any scenario in Table 7.1-1) and standard deviation = 2.3 for mirabegron group.
- 2. Obtain the treatment difference between mirabegron group and placebo group using mean difference (mirabegron minus placebo) as fixed effect described in formula (2) based on the generated data.
- 3. Apply formula (1) using $\sigma = 2.3$ to calculate the predictive probability of {final one-sided p-value of mirabegron vs. placebo ≤ 0.05 }, where for the interim evaluation N = 41, and M = 41.
- 4. If the futility criteria are not met, then generate for each treatment group data for 41 subjects to complete the trial.
- 5. Repeat Step 1-4 50,000 times (i.e., 50,000 simulated trials) for each scenario. Count the number of simulated trials which meet the futility criterion. In simulation, as long as mirabegron group meets the futility criterion, the simulated trial will be stopped. The probability of meeting the futility criterion for a given scenario is the percentage of the trials meeting the futility criterion out of the 50,000 simulated trials. Likewise, the probability of success is the percentage of the trials continuing to the end and having final 1-sided p-value of mirabegron vs. placebo ≤ 0.05 .

The above simulation procedure was performed for a number of treatment difference scenarios. The simulations were conducted using the software package SAS®.

3.1 Operating Characteristics

Table 7.1-2 presents the probabilities of futility at the interim evaluation, as well as the probability of success (defined as continuing to the end and having final 1-sided p-value of mirabegron vs. placebo ≤ 0.05), for each treatment difference scenario. In each treatment

difference scenario, we assume the common standard deviation of mean change from baseline to week 12/EoT in mean number micturitions per 24 hours is 2.3.

Treatment difference mirabegron vs. placebo (δ)*	Pr (Futility)	Pr (Success)
0.0	0.501	0.050
-0.2	0.345	0.134
-0.4	0.217	0.289
-0.6	0.118	0.503
-0.8	0.057	0.713
-0.9	0.038	0.797

Table 7.1-2: Probability of Futility and Success, $\sigma = 2.3$

* Negative value of δ indicates favorable treatment effect.

When there is no treatment difference between the mirabegron and placebo group ($\delta = 0$), study success would be a false positive one. Table 7.1-2 shows that in 50.1% of the simulations the trial would stop for futility. Furthermore, 5.0% of the simulated trials continued to the end and had a 1-sided *p*-value ≤ 0.05 for the test to compare the mean changes between the mirabegron and placebo group. Therefore, the false positive rate for this scenario is 5.0%.

When the treatment difference is -0.9 mean number of micturitions per 24 hours, favoring mirabegron over placebo, the study would only be stopped for futility with a probability of 3.8%, whereas 79.7% of the simulated trials continued to the end and had a 1-sided p-value ≤ 0.05 .

In addition, a sensitivity analysis for the assumption regarding the common standard deviation of mean change from baseline to week 12 in mean number of micturitions per 24 hours was performed on the same six treatment difference scenarios as described in Table 7.1-1 to assess the robustness of the design. The probabilities of futility and success assuming $\sigma = 2.5$ for each of the treatment difference scenarios are presented in Table 7.1-3.

For the efficacious scenarios where mirabegron shows favorable treatment effect over placebo ($\delta < 0$), the probabilities of futility are relatively higher and the probabilities of success are relatively lower compared to the results assuming $\sigma = 2.3$. For example, when the treatment difference is -0.6 points favoring mirabegron over placebo, the probability of futility in this scenario is 14.3% as compared to 11.8% assuming $\sigma = 2.3$, and the probability of success is 44.6%, as compared to 50.3% assuming $\sigma = 2.3$.

Treatment difference mirabegron vs. placebo (δ)*	Pr (Futility)	Pr (Success)
0.0	0.501	0.052
-0.2	0.357	0.127
-0.4	0.234	0.260
-0.6	0.143	0.446
-0.8	0.073	0.646
-0.9	0.051	0.739

Table 7.1-3: Probability of Futility and Success, $\sigma = 2.5$

* Negative value of δ indicates favorable treatment effect.

9.5 Derivation of Formula to Calculate Bayesian Predictive Probability

Derivation of Formula (1) as presented in Section 6.9 is described below.

Suppose two arms, placebo group and mirabegron group. The following notations are used:

- μ_P and μ_A denote the mean change from Baseline to Week 12/EoT in mean number of micturitions per 24 hours for the placebo and mirabegron group, respectively.
- σ denotes the common standard deviation.
- In total 164 subjects will be randomized to each of the two arms and will be in the FAS. Let *NN* denotes the total sample size per arm planned for the study to have a baseline and a Week 12/EoT value for the mean number of micturitions per 24 hours, NN = 82.
- N_P and N_A denote the number of subjects observed, with data, at the interim analysis for the placebo and mirabegron group, respectively.
- M_P and M_A denote the number of subjects as yet unobserved at the interim analysis for the placebo and mirabegron group, respectively. $M_P = NN N_P = 82 N_P$, $M_A = NN N_A = 82 N_A$.

Suppose that:

- For placebo group: $Y_1, Y_2, \dots, Y_{N_P}, Y_{N_P+1}, \dots, Y_{NN} \sim i. i. d. N(\mu_P, \sigma^2)$.
- For mirabegron group: $X_1, X_2, \dots, X_{N_A}, X_{N_A+1}, \dots, X_{NN} \sim i. i. d. N(\mu_A, \sigma^2)$.

At the interim analysis when N_P and N_A subjects have their Week 12/EoT data for placebo group (i.e., y_1, y_2, \dots, y_{N_P} have been observed) and mirabegron group (i.e., x_1, x_2, \dots, x_{N_A} have been observed), respectively, the posterior distribution of μ_P and μ_A assuming noninformative priors are:

$$\mu_P | y_1, y_2, \cdots, y_{N_P} \sim N\left(\bar{y}_{N_P}, \frac{\sigma^2}{N_P}\right), \text{ where } \bar{y}_{N_P} = \frac{1}{N_P} \sum_{i=1}^{N_P} y_i.$$
$$\mu_A | x_1, x_2, \cdots, x_{N_A} \sim N\left(\bar{x}_{N_A}, \frac{\sigma^2}{N_A}\right), \text{ where } \bar{x}_{N_A} = \frac{1}{N_A} \sum_{i=1}^{N_A} x_i.$$

For placebo group, the mean of as yet unobserved future data $Y_{N_P+1}, Y_{N_P+2} \cdots, Y_{N_N}$ is denoted as $\overline{Y}_{M_P}, \overline{Y}_{M_P} = \frac{1}{M_P} \sum_{i=N_P+1}^{N_N} Y_i$. The expectation and variance of \overline{Y}_{M_P} given observed data $y_1, y_2, \cdots, y_{N_P}$ can be expressed as follows

$$E(\bar{Y}_{M_P}|data) = E(E(\bar{Y}_{M_P}|\mu_P)|data) = E(\mu_P|data) = \bar{y}_{N_P}$$
$$Var(\bar{Y}_{M_P}|data) = Var(E(\bar{Y}_{M_P}|\mu_P)|data) + E(Var(\bar{Y}_{M_P}|\mu_P)|data)$$
$$= Var(\mu_P|data) + E\left(\frac{\sigma^2}{M_P}\right) = \frac{\sigma^2}{N_P} + \frac{\sigma^2}{M_P} = \sigma^2\left(\frac{1}{N_P} + \frac{1}{M_P}\right)$$

Astellas

Similarly for mirabegron group, the mean of as yet unobserved future data $X_{N_A+1}, X_{N_A+2}, \dots, X_{NN}$ is denoted as $\overline{X}_{M_A}, \overline{X}_{M_A} = \frac{1}{M_A} \sum_{i=N_A+1}^{NN} X_i$. The expectation and variance of \overline{X}_{M_A} given observed data x_1, x_2, \dots, x_{N_A} can be expressed as follows

$$E(\bar{X}_{M_A}|data) = E(E(\bar{X}_{M_A}|\mu_A)|data) = E(\mu_A|data) = \bar{x}_{N_A}$$
$$Var(\bar{X}_{M_A}|data) = Var(E(\bar{X}_{M_A}|\mu_A)|data) + E(Var(\bar{X}_{M_A}|\mu_A)|data)$$
$$= Var(\mu_A|data) + E\left(\frac{\sigma^2}{M_A}\right) = \frac{\sigma^2}{N_A} + \frac{\sigma^2}{M_A} = \sigma^2\left(\frac{1}{N_A} + \frac{1}{M_A}\right)$$

Hence the predictive distribution of \overline{Y}_{M_P} and \overline{X}_{M_A} given observed data are as follows

$$\bar{Y}_{M_P}|data \sim N\left(\bar{y}_{N_P}, \sigma^2\left(\frac{1}{N_P} + \frac{1}{M_P}\right)\right)$$
(1)

$$\bar{X}_{M_A} | data \sim N\left(\bar{x}_{N_A}, \sigma^2\left(\frac{1}{N_A} + \frac{1}{M_A}\right)\right)$$
(2)

Using (1) and (2), we have

$$\begin{split} E\left(M_{P}\bar{Y}_{M_{P}}-M_{A}\bar{X}_{M_{A}}|data\right) &= M_{P}\bar{Y}_{M_{P}}-M_{A}\bar{X}_{M_{A}}\\ Var\left(M_{P}\bar{Y}_{M_{P}}-M_{A}\bar{X}_{M_{A}}|data\right) &= M_{P}^{2}Var\left(\bar{Y}_{M_{P}}|data\right)+M_{A}^{2}Var\left(\bar{X}_{M_{A}}|data\right)\\ &= \sigma^{2}M_{P}^{2}\left(\frac{1}{N_{P}}+\frac{1}{M_{P}}\right)+\sigma^{2}M_{A}^{2}\left(\frac{1}{N_{A}}+\frac{1}{M_{A}}\right)\\ &= \sigma^{2}\left[M_{P}^{2}\left(\frac{N_{P}+M_{P}}{N_{P}M_{P}}\right)+M_{A}^{2}\left(\frac{N_{A}+M_{A}}{N_{A}M_{A}}\right)\right]\\ &= \sigma^{2}\left(M_{P}^{2}\frac{NN}{N_{P}M_{P}}+M_{A}^{2}\frac{NN}{N_{A}M_{A}}\right)\\ &= \sigma^{2}NN\left(\frac{M_{P}}{N_{P}}+\frac{M_{A}}{N_{A}}\right)\end{split}$$

Hence, the predictive distribution of $(M_P \overline{Y}_{M_P} - M_A \overline{X}_{M_A})$ given observed data is

$$M_{P}\bar{Y}_{M_{P}} - M_{A}\bar{X}_{M_{A}}|data \sim N\left(M_{P}\overline{y}_{N_{P}} - M_{A}\overline{x}_{N_{A}}, \sigma^{2}NN\left(\frac{M_{A}}{N_{A}} + \frac{M_{P}}{N_{P}}\right)\right)$$
(3)

We are interested in predicting whether the as yet unobserved future data together with the observed data will result in a one-sided *p*-value for the null hypothesis(H_0): $\mu_A - \mu_P \ge 0$, and the alternative hypothesis (H_1): $\mu_A - \mu_P < 0$. The standard test for testing H_0 versus H_1 at significance level $\alpha = 0.05$ is to reject H_0 if

$$\frac{\bar{Y}_{NN} - \bar{X}_{NN}}{\sigma \sqrt{\frac{2}{NN}}} > z_{0.95} \tag{4}$$

Now we compute the predictive probability of the rejection set in (4), which is denoted as *PP*.

$$PP = \Pr\left\{\frac{\overline{Y}_{NN} - \overline{X}_{NN}}{\sigma\sqrt{\frac{2}{NN}}} > z_{0.95}\right\}$$
$$= \Pr\left\{\overline{Y}_{NN} - \overline{X}_{NN} > z_{0.95}\sigma\sqrt{\frac{2}{NN}}\right\}$$
$$= \Pr\left\{\frac{N_P \overline{y}_{NP} + M_P \overline{Y}_{MP}}{NN} - \frac{N_A \overline{x}_{NA} + M_A \overline{X}_{MA}}{NN} > z_{0.95}\sigma\sqrt{\frac{2}{NN}}\right\}$$

Note that the observed \bar{y}_{N_P} and \bar{x}_{N_A} are fixed, but the as yet unobserved $(\bar{Y}_{M_P} - \bar{X}_{M_A})$ are random following the predictive distribution specified in (3). Therefore,

$$\begin{split} PP &= \Pr\left\{ \left(M_{P} \bar{Y}_{M_{P}} - M_{A} \bar{X}_{M_{A}} \right) + \left(N_{P} \bar{y}_{N_{P}} - N_{A} \bar{x}_{N_{A}} \right) > z_{0.95} \sigma NN \sqrt{\frac{2}{NN}} \right\} \\ &= \Pr\left\{ M_{P} \bar{Y}_{M_{P}} - M_{A} \bar{X}_{M_{A}} > z_{0.95} \sigma \sqrt{2NN} - \left(N_{P} \bar{y}_{N_{P}} - N_{A} \bar{x}_{N_{A}} \right) \right\} \\ &= \Pr\left\{ \frac{\left(M_{P} \bar{Y}_{M_{P}} - M_{A} \bar{X}_{M_{A}} \right) - \left(M_{P} \overline{y}_{N_{P}} - M_{A} \overline{x}_{N_{A}} \right)}{\sigma \sqrt{NN} \left(\frac{M_{A}}{N_{A}} + \frac{M_{P}}{N_{P}} \right)} \right\} \\ &> \frac{z_{0.95} \sigma \sqrt{2NN} - \left(N_{P} \bar{y}_{N_{P}} - N_{A} \bar{x}_{N_{A}} \right) - \left(M_{P} \overline{y}_{N_{P}} - M_{A} \overline{x}_{N_{A}} \right)}{\sigma \sqrt{NN} \left(\frac{M_{A}}{N_{A}} + \frac{M_{P}}{N_{P}} \right)} \right\} \\ &= \Pr\left\{ \frac{\left(M_{P} \bar{Y}_{M_{P}} - M_{A} \bar{X}_{M_{A}} \right) - \left(M_{P} \overline{y}_{N_{P}} - M_{A} \overline{x}_{N_{A}} \right)}{\sigma \sqrt{NN} \left(\frac{M_{A}}{N_{A}} + \frac{M_{P}}{N_{P}} \right)} \right\} \\ &> \frac{z_{0.95} \sigma \sqrt{2NN} - NN \left(\bar{y}_{N_{P}} - \bar{x}_{N_{A}} \right)}{\sigma \sqrt{NN} \left(\frac{M_{A}}{N_{A}} + \frac{M_{P}}{N_{P}} \right)} \right\} \end{split}$$

$$= \Pr\left\{\frac{\left(M_{P}\overline{Y}_{M_{P}} - M_{A}\overline{X}_{M_{A}}\right) - \left(M_{P}\overline{y}_{N_{P}} - M_{A}\overline{x}_{N_{A}}\right)}{\sigma\sqrt{NN\left(\frac{M_{A}}{N_{A}} + \frac{M_{P}}{N_{P}}\right)}}\right\}$$
$$> \frac{z_{0.95}\sigma\sqrt{2} - \sqrt{NN}(\overline{y}_{N_{P}} - \overline{x}_{N_{A}})}{\sigma\sqrt{\frac{M_{A}}{N_{A}} + \frac{M_{P}}{N_{P}}}}\right\}$$

From (3) we have

$$M_{P}\overline{Y}_{M_{P}} - M_{A}\overline{X}_{M_{A}} | data \sim N \left(M_{P}\overline{y}_{N_{P}} - M_{A}\overline{x}_{N_{A}}, \sigma^{2}NN \left(\frac{M_{A}}{N_{A}} + \frac{M_{P}}{N_{P}} \right) \right)$$

Let $Z = \frac{\left(M_{P}\overline{Y}_{M_{P}} - M_{A}\overline{X}_{M_{A}} \right) - \left(M_{P}\overline{y}_{N_{P}} - M_{A}\overline{x}_{N_{A}} \right)}{\sigma \sqrt{NN \left(\frac{M_{A}}{N_{A}} + \frac{M_{P}}{N_{P}} \right)}}, \quad Z \sim N(0,1)$

Hence,

$$\begin{split} PP &= \Pr\left\{ Z > \frac{z_{0.95}\sigma\sqrt{2} - \sqrt{NN}(\bar{y}_{N_P} - \bar{x}_{N_A})}{\sigma\sqrt{\frac{M_A}{N_A} + \frac{M_P}{N_P}}} \right\} \\ &= \Pr\left\{ Z > \sqrt{\frac{2}{\frac{M_A}{N_A} + \frac{M_P}{N_P}} \left[z_{0.95} - \sqrt{NN}\frac{\bar{y}_{N_P} - \bar{x}_{N_A}}{\sqrt{2}\sigma} \right] \right\} \\ &= 1 - \Pr\left\{ Z \le \sqrt{\frac{2}{\frac{M_A}{N_A} + \frac{M_P}{N_P}} \left[z_{0.95} - \sqrt{NN}\frac{\bar{y}_{N_P} - \bar{x}_{N_A}}{\sqrt{2}\sigma} \right] \right\} \\ &= 1 - \Phi\left\{ \sqrt{\frac{2}{\frac{M_A}{N_A} + \frac{M_P}{N_P}} \left[z_{0.95} - \sqrt{NN}\frac{\bar{y}_{N_P} - \bar{x}_{N_A}}{\sqrt{2}\sigma} \right] \right\} \\ &= \Phi\left\{ \sqrt{\frac{2}{\frac{M_A}{N_A} + \frac{M_P}{N_P}} \left[z_{0.95} - \sqrt{NN}\frac{\bar{y}_{N_P} - \bar{x}_{N_A}}{\sqrt{2}\sigma} \right] \right\} \end{split}$$

By substituting *NN* by 82, M_A by 82 – N_A , M_P by 82 – N_P , and σ by $\hat{\sigma}$, we have

Astellas

$$PP = \Phi \left\{ \sqrt{\frac{2}{\frac{82 - N_A}{N_A} + \frac{82 - N_P}{N_P}}} \left[\sqrt{82} \frac{\bar{y}_{N_P} - \bar{x}_{N_A}}{\sqrt{2}\hat{\sigma}} - z_{0.95} \right] \right\}$$

where

- Φ stands for the cumulative distribution function for the standard normal distribution.
- \bar{y}_{N_P} and \bar{x}_{N_A} are the LS means for placebo group and mirabegron group, respectively, and will be obtained from the ANCOVA model (using LOCF), described in Section 6.4.1.1 of the SAP.
- $\hat{\sigma}$ is the estimated pooled standard deviation and will be obtained from the same ANCOVA model as described above.

Note that when the numbers of subjects observed at the interim analysis for the mirabegron and placebo group are equal (i.e., $N_A = N_P = N$), let M = NN - N = 82 - N, the formula can be simplified to

$$PP = \Phi\left\{\sqrt{\frac{1}{M}}\left[\sqrt{82}\frac{\bar{y}_{N_P} - \bar{x}_{N_A}}{\sqrt{\frac{2}{N}}\hat{\sigma}} - \sqrt{N}z_{0.95}\right]\right\},\label{eq:PP}$$

which is the same as the one used in the Appendix 9.4.

9.6 Interim Analysis Report Template

Study 178-CL-204 Interim Analysis Futility Analysis Results Generated by [IDAC Statistician's Full Name] on ddMMMyyyy

The performed Interim Analysis should determine if the chance of a positive study with respect to the primary endpoint at the final analysis is high enough to justify continuation of the study (Predictive Probability is ≥ 0.05); otherwise, the study should be stopped for futility.

Based on the following statistics calculated using the data by the cut-off date *ddMMMyyyy*:

- The number of subjects observed at the interim analysis for placebo and mirabegron group are *XX* and *XX*, respectively.
- The least squares means for placebo group and mirabegron group are *XX.X* and *XX.X*, respectively, for the mean change from baseline in mean number of micturitions per 24 hours at week12/EoT. The results are obtained from an ANCOVA model with treatment group, sex and geographical region as fixed effects and the mean number of micturitions per 24 hours at baseline as covariate. This analysis was performed with imputation of missing visit 7/week 12 data using the last observation carried forward (LOCF) method.
- The estimated pooled standard deviation is *XX.X*, obtained from the same ANCOVA model as described above.

Predictive Probability of ({final one-sided p-value of mirabegron vs. placebo ≤ 0.05 }|Data) = 0.XXX

Hence, the study [did or did not] meet the futility criteria "Predictive Probability is ≥ 0.05 ". The IDAC recommends the study to [continue or stop].

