9.10 Interim Analysis (and Early Discontinuation of the Study)

A blinded interim analysis will be performed after 50% of children planned to be randomized have had their week 12/EoT assessment. The interim analysis will determine if the chance of a positive study with respect to the primary endpoint at the EoS is high enough to justify continuation of the study; otherwise, the study will be stopped for futility.

Given the data at the interim analysis, the independent data analysis center (IDAC) will calculate the predictive probability of a positive study. A positive study is defined as the final 1-sided p-value ≤ 0.05 when comparing Mirabegron vs. placebo in the primary efficacy analysis (in children [5 to \leq 12 years of age]). If the predictive probability is \leq 5% at this interim evaluation, the study will be recommended to stop for futility. Otherwise, the study will continue.

Detailed information on the decision rule of futility and simulations illustrating the operating characteristics of futility criterion will be presented in the SAP.

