6.9 Interim Analysis (and Early Discontinuation of the Clinical Study)

One comparative interim analysis will be performed after 50% of children planned to be randomized have had their week 12/EoT assessment. Only data from those children with week 12/EoT assessment will be used in the interim analyses. The interim analysis will determine if the chance of a positive study with respect to the primary endpoint at the final analysis is high enough to justify continuation of the study; otherwise, the study will be stopped for futility.

Given the data at the interim analysis, a predictive probability of a positive study will be calculated. A positive study is defined as the final 1-sided p-value ≤ 0.05 when comparing mirabegron vs. placebo in the primary efficacy analysis (in children [5 to < 12 years of age]).

If the predictive probability is $\leq 5\%$ at this interim evaluation, the study will be recommended to stop for futility. Otherwise, the study will continue.

No efficacy analyses will be performed except for determination of futility.

At the interim analysis, the following predictive probability will be calculated: Predictive Probability of ({final one-sided p-value of mirabegron vs. placebo ≤ 0.05 } |Data).

Since we use non-informative prior distribution of difference in mean change from Baseline to week 12/EoT in mean number of micturitions per 24 hours between the mirabegron group and the placebo group and assume the mean change from Baseline to week 12/EoT in mean number of micturitions per 24 hours follows a Gaussian distribution, the Bayesian predictive probability for the event of a final one-sided p-value of mirabegron vs. placebo ≤ 0.05 (denoted by *PP*) can be obtained using a closed form based on the methods described in Geisser and Johnson (1994), Spiegelhalter etc. (2004), Dmitrienko and Wang (2006). Appendix 9.5 contains a detailed derivation.

$$PP = \Phi \left\{ \sqrt{\frac{2}{\frac{M_P}{N_P} + \frac{M_A}{N_A}}} \left[\sqrt{82} \frac{\overline{y}_{N_P} - \overline{x}_{N_A}}{\sqrt{2}\hat{\sigma}} - z_{0.95} \right] \right\}$$
(1)

where

- Φ stands for the cumulative distribution function for the standard Gaussian distribution. $\Phi(Z_{0.95}) = 0.95$.
- N_P and N_A denote the number of subjects observed at the interim analysis for placebo group and mirabegron group, respectively.

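### The SAP 9.6 report template names PP ≥ 0.05 as the futility criterion and Appendix 9.4 formula (2) has the wrong sign; either one, read literally on its own, reverses the Section 6.9 futility rule

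*SAP*

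**What the plan says.** **The rule.** For a PP of 5% or less, SAP 6.9 states that "at this interim evaluation, the study will be recommended to stop for futility. Otherwise, the study will continue". Appendix 9.4, section 2.1, says the same: "If the predictive probability is no more than 0.05 at this interim evaluation, the study will be recommended to stop for futility". Protocol 9.10 has the same threshold and direction. A positive study is one with a final one-sided p-value of 0.05 or less.

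**The formula.** SAP 6.9 and the final formula in Appendix 9.5 compute PP from the placebo mean change minus the mirabegron mean change. Appendix 9.4, section 1.0, treats a negative change as beneficial, so this difference is positive when mirabegron works.

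**The passages that differ.**

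- The 9.6 template opens by asking whether the chance of a positive study is "high enough to justify continuation of the study (Predictive Probability is ≥ 0.05); otherwise, the study should be stopped for futility". Its conclusion line then reads "the study [did or did not] meet the futility criteria 'Predictive Probability is ≥ 0.05".
- Appendix 9.4, section 2.2, formula (2), gives the numerator of Z_N as "Difference in LS mean change (mirabegron - placebo", and formula (1) uses Z_N with a plus sign. Step 2 of the simulation algorithm repeats the direction: "using mean difference (mirabegron minus placebo) as fixed effect described in formula (2".
- Appendix 9.5 closes by saying that its equal-arms formula is the one used in Appendix 9.4.
- Appendix 9.4, section 2.2, takes the LS means from a model with "visit, geographical region, sex, and treatment by visit interaction as fixed effects" in addition to treatment. SAP 6.9 names the Section 6.4.1.1 ANCOVA, and 9.5 and 9.6 add that it uses LOCF.

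**The concern.** The futility rule is the only efficacy-based rule that can end the trial early. The 9.6 template is the form on which the Independent Data Analysis Center (IDAC) sends its recommendation to the sponsor's decision-maker, and Section 6.9 refers readers to Appendix 9.4 for detail on the decision rule.

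Completed as printed, the template would record a promising interim as having met the futility criteria, beside a recommendation to continue. Programmed as printed, formula (2) would give a low PP to an effective drug and a high PP to a harmful one. The IDAC develops its programs before the data cut-off, and only its statistician holds the treatment codes. Blinded sponsor staff therefore cannot check the direction of the calculation while the trial is running.

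**Working it through.** **Inputs.** Appendix 9.4: SD 2.3; planned 82 per arm; interim N = 41 observed and M = 41 still to come per arm; δ = mirabegron − placebo, negative being favourable. Final criterion z0.95 = 1.645.

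**Step 1: reduce the rule.** Formula (1) in 9.4 is PP = Φ{[√(N+M)·Z_N − √N·1.645]/√M}. With N = M = 41 this becomes PP = Φ(√2·Z_N − 1.645). Then PP ≤ 0.05 requires √2·Z_N − 1.645 ≤ −1.645, that is, Z_N ≤ 0. With Z_N taken as placebo − mirabegron, the rule stops when mirabegron looks no better than placebo. With the printed sign it stops when mirabegron looks no worse than placebo. The two are exact mirror images.

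**Step 2: reproduce Table 7.1-2.** The standard error of the interim difference is 2.3·√(2/41) = 0.508, so with the Section 6.9 sign Pr(stop) = Φ(δ/0.508). With the printed 9.4 sign it is 1 minus that.

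| δ | Table 7.1-2 | Section 6.9 sign | Formula (2) as printed |
|---|---|---|---|
| 0.0 | 0.501 | 0.500 | 0.500 |
| −0.2 | 0.345 | 0.347 | 0.653 |
| −0.4 | 0.217 | 0.216 | 0.784 |
| −0.6 | 0.118 | 0.119 | 0.881 |
| −0.8 | 0.057 | 0.058 | 0.942 |
| −0.9 | 0.038 | 0.038 | 0.962 |

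With the Section 6.9 sign, one million simulated trials per scenario reproduce all 12 rows of Tables 7.1-2 and 7.1-3 to within 0.006. The printed sign does not reproduce them.

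**Step 3: a single interim at the planned effect.** With an observed difference of −0.9, |Z_N| = 0.9/0.508 = 1.772.

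- Section 6.9: PP = Φ(√2 × 1.772 − 1.645) = Φ(0.861) = 0.805, so continue.
- Formula (2) as printed: PP = Φ(−√2 × 1.772 − 1.645) = Φ(−4.151) = 0.00002, so stop.

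At an observed +0.9, where mirabegron is worse, the two values swap.

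**Step 4: over repeated trials at δ = −0.9.** Success means continuing past the interim and reaching a final one-sided p ≤ 0.05. The interim and final statistics have correlation √0.5.

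| Reading | Pr(stop) | Pr(success) |
|---|---|---|
| Section 6.9 sign, stop if PP ≤ 0.05 | 0.038 | 0.798 |
| Section 6.9 sign, stop if PP ≥ 0.05 (9.6 line taken literally) | 0.962 | 0.007 |
| 9.4 sign, stop if PP ≤ 0.05 | 0.962 | 0.007 |
| Both reversals together | 0.038 | 0.798 |

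Table 7.1-2 states 0.038 and 0.797 for this scenario. As a check, power at 82 per arm with no interim is 0.805, and 0.798 + 0.007 = 0.805. The reversed rule keeps only the successes that the correct rule gives up.

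**Step 5: the 9.5 equality statement.** The equal-arms formula in 9.5 has placebo minus mirabegron in the numerator; formula (2) in 9.4 has mirabegron minus placebo. They agree in form but not in sign.

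**The case against.** The strongest reply is that nothing governing the decision is wrong. Section 6.9 is the body text that prescribes the calculation; its formula has the right sign, allows unequal arms, and cites Appendix 9.5 for the derivation. The decision rule in 9.4 is also stated correctly. The template does not say that meeting the criterion means stopping: the recommendation is a separate field, and the opening sentence of the same page gives the right direction. The report prints both LS means beside PP, so a clear benefit with a PP near zero would be conspicuous, and a person decides whether to stop. On this view the template mislabels the rule, and the 96.2% needs a reader who ignores both Section 6.9 and the opening sentence.

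Much of this stands. A reader who follows Section 6.9 gets the right answer, the published operating characteristics are unaffected, and the template alone is more likely to yield a self-contradictory report than a wrong stop. Two things remain. Appendix 9.4 itself uses meeting the futility criterion to mean stopping (section 2.0 and simulation step 5), so the literal reading of the template follows the SAP's own usage. And the sign in formula (2) is not an isolated slip, because step 2 repeats it and 9.5 vouches for it.

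**Conclusion.** The concern holds. The template's conclusion line contradicts Section 6.9 and its own opening sentence. Formula (2) conflicts in sign with the formulas in 6.9 and 9.5, so the 9.5 statement of equality is untrue. At the design assumptions (δ = −0.9, SD 2.3, 41 per arm at the interim, SD treated as known), either defect taken literally on its own moves the stopping probability from 3.8% to 96.2% and the success probability from 79.8% to 0.7%. The two together cancel. These figures bound the effect of a literal reading; they do not predict what the IDAC would do.

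Two smaller points belong with it. Appendix 9.4 names a different interim model from 6.9, 9.5 and 9.6; no size was calculated for that difference. At a PP of exactly 0.05, Section 6.9 stops while the template's opening sentence continues.

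**What to change.** 1. In 9.6, write the futility criterion in the conclusion line as PP ≤ 0.05 and the continuation condition in the opening sentence as PP > 0.05.
2. In 9.4, define Z_N in formula (2) as placebo minus mirabegron and match it in simulation step 2. Keeping δ as mirabegron minus placebo and negating it once, explicitly, would serve equally well. Either makes the 9.5 statement of equality true.
3. In 9.4, replace the model with visit and treatment-by-visit terms by the Section 6.4.1.1 ANCOVA with LOCF.
4. Check the sign in the penultimate line of the 9.5 derivation against the source PDF. The bracket looks reversed in the extracted text, which may be extraction damage; the final formula is right and nothing here depends on that line.
5. If the interim has already been run, confirm and document which formula, model and criterion were applied.

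The cost is SAP wording only. No simulation needs rerunning, because Tables 7.1-2 and 7.1-3 already correspond to the correct sign.
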